10. APPENDICES

10.1. APPENDIX 1: DATA DERIVATION DETAILS

Not applicable

10.2. APPENDIX 2: ADDITIONAL STATISTICAL METHODOLOGY DETAILS

Not applicable

10.3. APPENDIX 3: DIAGNOSIS AND PROCEDURE CODES USED IN THE STUDY

10.3.1. List of diagnosis code

Variable Used in Study	ICD-10 Code*	Additional rules on Data Extraction
Atrial fibrillation	I48	
Post-operative atrial fibrillation	8847772	Standard disease code
Valvular atrial fibrillation	8846941	Standard disease code
Rheumatic atrial fibrillation	105	
	106	
	I07	
	I08	
	I09	
Mechanical-valvular atrial fibrillation	T820	
Hyperthyroidism or thyrotoxicosis	E05	
Heart failure	I110	
	1500	
	I501	Exclude cardiac asthma
	1509	
Hypertension	H208	Include only hypertensive iridocyclitis
	H350	Include only hypertensive retinopathy and hypertensive neuroretinopathy
	I10	
	I110	
	I119	
	I120	
	I129	Include only hypertensive renal disease, hypertensive nephropathy and hypertensive nephrosclerosis
	I139	

Variable Used in Study	ICD-10 Code*	Additional rules on Data Extraction
¥	I150	
	I151	
	I152	
	I158	
	I159	
	I619	Include only hypertensive intracerebral hemorrhage
	I674	
Diabetes	E10	
	E11	
	E12	
	E13	
	E14	
Hemorrhage stroke	160	
	I61	
	I62	Exclude non-traumatic extradural haemorrhage
Ischemic stroke	I63	
	3489032	standard disease code
	4371003	-
	4379014	-
	3448002	-
	3448028	-
	3489029	-
	3489035	-
	4379006	-
TIA	H340	
	G450	
	G451	
	G458	
	G459	
Systemic embolism	1740	Include only abdominal aortic embolism
	I741	Include only aortic embolism
	I742	Include only acute arterial occlusive disease of arteries of upper extremities
	1743	Include only femoral arterial occlusion and acute arterial occlusive disease of arteries of lower extremities
	I744	
	1745	Include only iliac artery embolism
		ONFIDENTIAL

Variable Used in Study	ICD-10 Code*	Additional rules on Data Extraction
· · · · ·	I748	Include only hepatic artery embolism
	1749	Include only thromboembolism, embolic infarction, aortic embolism
Peripheral vascular disorder	1702	Include only atherosclerosis and arteriosclerosis obliterans
	I709	
	I731	Include only Buerger's disease
	1739	Exclude peripheral circulatory failure, cerebrovascular spasm, and angiospasm pf the extremities
	I742	
	I743	
	I745	
	I748	Include only subclavian artery stenosis
Aortic plaque	4400011	Standard disease code
	8837393	Standard disease code
Coronary artery disease	I200	
	I201	
	I208	
	I209	
	I210	
	I211	
	I212	
	I213	
	I214	
	I240	
	I241	
	I248	
	I251	
	1252	Exclude calcification of coronary artery
	1255	
	1258	Exclude coronary arteritis
	1259	
Myocardial infarction	1200	Exclude intermediate angina syndrome, preinfarction syndrome, initial arbeits angina, intermediate coronary syndrome
	I210	
	I211	
	I212	
	I214	

Variable Used	ICD-10 Code*	Additional rules
in Study	I240	on Data Extraction
	I241	Exclude Dressler syndrome
Renal impairment	I120	
	I120 I129	
	I129 I139	
	N003	
	N003	
	N032	
	N033	
	N039	
	N040	
	N044	
	N049	
	N052	
	N055	
	N058	
	N059	
	N170	
	N171	
	N172	
	N178	
	N179	
	N189	
	N19	Exclude renal anemia, afunctional kidney, and alimentary proteinuria
Liver dysfunction	B150	
	B159	
	B162	
	B169	
	B171	
	B172	
	B178	
	B179	
	B181	
	B182	
	B189	
	B190	
	B199	
		20NEIDENTI AI

Variable Used in Study	ICD-10 Code*	Additional rules on Data Extraction
In Study	C220	
	K700	
	K701	
	K703	
	K709	
	K716	
	K720	
	K721	
	K729	
	K730	
	K732	
	K738	
	K739	
	K740	
	K741	
	K743	
	K744	
	K745	
	K746	
	K750	
	K751	
	K754	
	K759	
	K760	
	K761	
	K762	
	K763	
	K766	
	K767	
	K768	
	K769	
Cancer	C00	
	C01	
	C02	
	C03	
	C04	
	C05	

Variable Used in Study	ICD-10 Code*	Additional rules on Data Extraction
	C06	
	C07	
	C08	
	C09	
	C10	
	C11	
	C12	
	C13	
	C14	
	C15	
	C16	
	C17	
	C18	
	C19	
	C20	
	C21	
	C22	
	C23	
	C24	
	C25	
	C26	
	C30	
	C31	
	C32	
	C33	
	C34	
	C37	
	C38	
	C40	
	C41	
	C43	
	C44	
	C45	
	C46	
	C47	
	C48	

Variable Used in Study	ICD-10 Code*	Additional rules on Data Extraction
	C49	
	C50	
	C51	
	C52	
	C53	
	C54	
	C55	
	C56	
	C57	
	C58	
	C60	
	C61	
	C62	
	C63	
	C64	
	C65	
	C66	
	C67	
	C68	
	C69	
	C70	
	C71	
	C72	
	C73	
	C74	
	C75	
	C76	
	C78	
	C79	
	C80	
	C81	
	C82	
	C83	
	C84	
	C85	
	C88	

Variable Used in Study	ICD-10 Code*	Additional rules on Data Extraction
	C90	
	C91	
	C92	
	C93	
	C94	
	C95	
	C96	
	C97	
	D00	
	D01	
	D02	
	D03	
	D04	
	D05	
	D06	
	D07	
	D09	
	D10	
	D11	
	D12	
	D13	
	D14	
	D15	
	D16	
	D17	
	D18	
	D19	
	D20	
	D21	
	D22	
	D23	
	D24	
	D25	
	D27	
	D28	
	D29	

Variable Used in Study	ICD-10 Code*	Additional rules on Data Extraction
	D30	
	D31	
	D32	
	D33	
	D34	
	D35	
	D36	
	D37	
	D38	
	D39	
	D40	
	D41	
	D42	
	D43	
	D44	
	D45	
	D46	
	D48	

10.3.2. List of procedure code

Procedure	Procedure Code
Cardiac surgery	150138210
	150138310
	150138410
	150138510
	150359210
	150138710
	150140510
	150140610
	150140710
	150139010
	150140810
	150318010
	150317810
	150318110
	150331450

Procedure	Procedure Code
	150331550
	150331950
	150332050
	150317910
	150318210
	150140010
	150139210
	150153910
	150374910
	150375010
	150375110
	150260350
	150284310
	150359310
	150263310
	150375210
	150375310
	150375410
	160107550
	150139810
	150139910
	150318310
	150145710
	150145810
	150145910
	150146010
	150318410
	150318510
	150302770
	150143010
	150143110
	150331650
	150332150
	150318710
	150319010
	150319310
	150318810
	150319110

Procedure	Procedure Code
	150319410
	150328750
	150328850
	150331750
	150331850
	150332250
	150332350
	150318910
	150319210
	150319510
	150318610
	150141010
	150279510
	150279610
	150141410
	150141610
	150369950
	150141710
	150359470
	150143610
	150260050
	150143710
	150143810
	150141510
	150375570
	150375670
	150375770
	150319610
	150292910
	150139310
	150140910
	150242550
	150244910
	150245010
	150359510
	150359610
	150381150
	150381250

Procedure	Procedure Code
	150381350
	150381450
	150150010
	150381550
	150275910
	150359710
	150359810
	150359910
	150381650
	150381750
	150381850
	150381950
	150150110
	150382050
	150245110
	150245210
	150375870
	150375970
	150376070
	150141210
	150301310
	150267850
	150319710
	150151810
	150376110
	150139110
	150319810
	150138810
	150151910
	150320010
	150346410
	150320110
	150147150
	150144110
	150320210
	150320310
	150142710
	150139410

Procedure	Procedure Code
	150320410
	150142910
	150320510
	150260150
	150346510
	150145110
	150145010
	150376210
	150376310
	150143250
	150143350
	150143450
	150143550
	150283250
	150283350
	150283450
	150283550
	150144910
	150139610
	150142410
	150141810
	150141910
	150320610
	150142050
	150142110
	150142210
	150142310
	150142810
	150144010
	150320710
	150144210
	150144550
	150147410
	150147510
	150320810
	150320910
	150144410
	150144650

Procedure	Procedure Code
	150144750
	150146510
	150146610
	150321010
	150321110
	150321210
	150376470
	150146910
	150146810
	150321310
	150142510
	150329810
	150145310
	150329910
	150139510
	150330010
	150147010
	150330110
	150376570
	150321410
	150321510
	150376670
	150147310
	150145650
	150141310
	150321810
	150321610
	150321910
	150146710
	150321710
	150330210
	150330310
	150376770
	150293010
	150330410
	150145510
	150302870
	150145410

Procedure	Procedure Code
	150322010
	150322110
	150144310
	150147250
	150346610
	150144810
	150253810
	150253910
	150275610
	150346710
	150262810
	150303310
	150267310
	150140110
	150140210
	150140410
	150346910
	150347010
	150303210
	150322210
	150275210
	150275310
	150336910
	150337010
	150360010
	150148010
	150148110
	150147610
	150147910
	150147770
	150147870
	150347170
	150275870
	150262910
	150275710
	150266110
	150382650
	150266210

Procedure	Procedure Code
	150382750
	150301810
	150382850
	150303410
	150303510
	150360110
	150360210
	150360310
	150360410
	150303610
	150303710
	150322410
	150322610
Ablation	150346710
	150262810
	150303310
	150346870
	150370050
Electrical defibrillation	140051410
	140010310
	140055010
	150275210
	150275310
	150336910
	150337010
	150370550
Heart valve prosthesis implantation surgery	150141410
	150141610
	150141710
	150359470
	150369950
	150331950
	150332050
	150332150
	150328850
	150332250
	150332350
	150141510

Procedure	Procedure Code
	150375570
	150375670
	150375770
	150244910
	150359510
	150381150
	150381250
	150359710
	150359810
	150381650
	150381750
	150283450

10.3.3. Effectiveness endpoints

Disease	ICD10 code	Standard disease code	Note
	I60		
Hemorrhage	I61		
stroke	I62		Exclude non-traumatic extradural haemorrhage
	I63		
		3489032	
		4371003	
		4379014	
Ischemic stroke		3448002	
		3448028	
		3489029	
		3489035	
		4379006	
	H340		
	G450		
TIA	G451		
	G458		
	G459		
	I740		Include only abdominal aortic embolism
	I741		Include only aortic embolism
	I742		Include only acute arterial occlusive disease of arteries of
			upper extremities
Systemic embolism	I743		Include only femoral arterial occlusion and acute arteria
			occlusive disease of arteries of lower extremities
	I744		
	I745		Include only iliac artery embolism
	I748		Include only hepatic artery embolism
	I749		Include only thromboembolism, embolic infarction, aorti
			embolism

Page 43 of 56

Disease	ICD10 code	Standard disease code	Note	
	I748		Include only subclavian artery stenosis	

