3.2. STATISTICAL DECISION RULES

For primary safety and effectiveness analyses, all statistical tests will be performed at p=0.05 (twosided) with no adjustment for multiplicity. Since we will conduct various multiple subgroup analyses, which lead to the "Multiple Testing Problem". Here these subgroup analyses will be conducted with an exploratory purpose and we do not plan to conclude anything from the results here. Therefore, we will not adjust the p values and still the use p<0.05 to indicate the statistical significance.

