5. ENDPOINTS AND COVARIATES

5.1. EFFICACY/EFFECTIVENESS ENDPOINT(S)

Variable	Role	Operational definition		
Stroke/SE (composite) event after index date	Outcome (primary endpoint)	Operational definition of Stroke and SE will follow the operational definition of Stroke event after index date and SE event after index date. Time to events will be defined as the number of days from the index date to the occurrence of the first stroke or SE.		
Ischemic stroke event after index date	Outcome (secondary endpoint)	Ischemic stroke after index date not including the index date will be identified using hospital claims which had an ischemic stroke diagnosis code as the first listed ICD-10 diagnosis code (Appendix, 10.3.3). An event occurrence of ischemic stroke is defined as a case that "01: Disease name which input the most medical resources", "02:Sub-disease name", "11: Main disease name", "21: Disease name behind hospitalization", or "31: Disease name which input the second most medical resources" in DPC database. Time to ischemic		

Variable	Role	Operational definition	
		stroke will be defined as the number of days from the index date to the occurrence of the first ischemic stroke.	
Hemorrhagic stroke event after index date	Outcome (secondary endpoint)	Hemorrhagic stroke after index date not including the index date will be identified using hospital claims which had a hemorrhagic stroke diagnosis code as the first listed ICD-10 diagnosis code (Appendix, 10.3.3). An event occurrence of hemorrhagic stroke i defined as a case that "01: Disease name which input the most medical resources", "02:Sub-disease name", "11: Main disease	
SE event after index date Outcome (secondary endpoint)		SE after index date not including the index date will be identified using hospital claims which had a SE diagnosis code as the first listed ICD-10 diagnosis code (Appendix, 10.3.3). An event occurrence of SE is defined as a case that "01: Disease name which input the most medical resources", "02:Sub-disease name", "11: Main disease name", "21: Disease name behind hospitalization", or "31: Disease name which input the second most medical resources" in DPC database. Time to SE will be defined as the number of days from the index date to the occurrence of the first SE event.	

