7. STATISTICAL METHODOLOGY AND STATISTICAL ANALYSES

7.1. STATISTICAL METHODS

7.1.1. Calculation of Propensity Score

In this study, balanced cohorts (apixaban vs. warfarin) will be created by an IPTW method. Propensity scores will be estimated by unconditional logistic regression analyses that incorporate potential predictors of therapy as independent variables in the regression and cohort status as the outcome. Using calculated propensity score an IPTW method will be applied to balance the warfarin and apixaban cohorts, which will be used for the comparisons of all endpoints (sections 5.1 and 5.2). The following covariates will be included in the logistic regression for calculation of propensity score:

• age on index date

- gender
- CHADS2 score in baseline
- CHA2DS2-VASc score in baseline
- heart failure diagnosis in baseline
- coronary heart disease diagnosis in baseline
- peripheral arterial disorder diagnosis in baseline
- myocardial infarction diagnosis in baseline
- hyperthyroidism or thyrotoxicosis in baseline
- TIA diagnosis in baseline
- stroke or SE diagnosis in baseline
- renal dysfunction diagnosis in baseline
- liver dysfunction diagnosis in baseline
- bleeding diagnosis in baseline
- hypertension diagnosis in baseline
- diabetes mellitus diagnosis in baseline
- treated with antiplatelet drug in baseline
- treated with NSAIDs in baseline
- treated with gastric secretion inhibitor in baseline
- treated with statin-based drug in baseline
- treated with anti-hypertensives in baseline
- treated with anti-arrhythmics in baseline
- treated with beta-blockers in baseline
- treated with heparins in baseline
- cardioversion in baseline

The operational definitions for the above covariates are shown in the Section 5.4.

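### The SAP's effectiveness code list prints a subclavian artery stenosis row straight after the systemic embolism block; programmed as printed, a non-embolic condition would count in SE and the primary stroke/SE composite

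*SAP*

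**What the plan says.** SAP 5.1 identifies an SE event from "hospital claims which had a SE diagnosis code as the first listed ICD-10 diagnosis code (Appendix, 10.3.3"), counting from the day after the index date and listing five DPC disease-name fields. The primary composite has no code list of its own: "Operational definition of Stroke and SE will follow the operational definition of Stroke event after index date and SE event after index date". SE is also a secondary endpoint. SAP 7.2.3 gives it its own Cox model, Kaplan-Meier plot and incidence rate.

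In SAP 10.3.3 the systemic embolism block runs from I740 to I749. Within it, I748 carries the note "Include only hepatic artery embolism". After I749 come a page break and a repeated column header, then a single further row: I748, "Include only subclavian artery stenosis". Its Disease cell is empty and no other disease label precedes it.

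In SAP 10.3.1 the systemic embolism block has the same codes and stops at I749. The I748 subclavian row appears there too, but as the last row of the block labelled "Peripheral vascular disorder". The propensity model in SAP 7.1.1 includes "peripheral arterial disorder diagnosis in baseline" as a covariate.

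**The concern.** Two lists that should define the same concept disagree, and the one that differs is the one 5.1 names for the outcome. Every other restricted row in the SE block describes an embolism, an arterial occlusion or an infarction. This one describes a stenosis, a narrowing of the vessel rather than an embolic event.

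If the row is used, hospital claims for subclavian stenosis become SE events and then primary composite events. The SAP excludes only the index date, and no eligibility criterion removes patients with existing peripheral arterial disease. A long-standing stenosis coded at a later admission could therefore be counted as a new event. The same disease name would also feed a baseline covariate, assuming that the peripheral vascular disorder list in 10.3.1 is the one behind the peripheral arterial disorder variable; the names differ slightly, but no other list fits. Events unrelated to anticoagulation would dilute the comparison, most of all in the SE endpoint taken alone.

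**Working it through.** **1. The two lists side by side**

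| Item | SAP 10.3.1 | SAP 10.3.3 |
|---|---|---|
| SE block, I740 to I749 | present | present |
| I748, hepatic artery embolism only | in the SE block | in the SE block |
| I748, subclavian artery stenosis only | last row of peripheral vascular disorder | last row of the table, after the SE block, Disease cell empty |

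Both tables print a disease label once per block and leave the cell empty on the block's other rows. An empty cell is therefore how a continuing block normally looks. With no new label, the literal reading is that the row belongs to systemic embolism.

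**2. The plan's own stroke/SE figures (SAP 7.1.9)**

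Inputs: HR 0.7, two-sided alpha 0.05, power 0.80, allocation 1:1, rates 2.77 and 1.79 %/year.

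- Events = 4(z₀.₉₇₅ + z₀.₈₀)² / (ln 0.7)² = 4(1.960 + 0.842)² / (0.3567)² = 246.8, or 247 rounded up. The SAP states 246.
- Patients = 246 / [(0.0277 + 0.0179)/2] = 246 / 0.0228 = 10,789. The SAP states 10,789, which implies one person-year per patient.

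The figures reproduce. None of them depends on the disputed row.

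**3. Illustration for the SE endpoint**

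The documents give no count of subclavian stenosis codes, so the share s below is an assumption. Set the true SE rate to 1 on warfarin and 0.70 on apixaban, with equal person-time, so the mean is 0.85. Let stenosis codes occur at rate F in both arms and make up a share s of all counted SE events.

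- s = F/(0.85 + F), so F = 0.85s/(1 − s). Observed HR = (0.70 + F)/(1 + F).
- s = 10%: F = 0.85 × 0.1/0.9 = 0.094; HR = 0.794/1.094 = 0.726, about 0.73.
- s = 30%: F = 0.85 × 0.3/0.7 = 0.364; HR = 1.064/1.364 = 0.780, about 0.78.

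**4. Illustration for the primary composite**

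Here f, also assumed, is the share of warfarin-arm composite events that are stenosis codes with HR 1. The rest have HR 0.7, so HR = 0.7(1 − f) + f.

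| f | Composite HR | Events for 80% power | Power at 246 events |
|---|---|---|---|
| 0 | 0.700 | 247 | 79.9% |
| 1% | 0.703 | 253 | 78.9% |
| 2% | 0.706 | 260 | 77.9% |
| 5% | 0.715 | 279 | 74.9% |
| 10% | 0.730 | 317 | 69.4% |

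The shares in steps 3 and 4 have different denominators and should not be compared directly.

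**The case against.** The strongest reply is that the row is clerical debris. Its Disease cell is empty, it stands alone after a page break, and it is out of code order behind I749. The SE block above it is already complete with its own restricted I748 row. The same row closes the peripheral vascular disorder block in 10.3.1, so a leftover from that list is plausible. This stands to the extent that assignment to SE rests on table position. A reader might infer that the SAP definitely counts subclavian stenosis in the primary composite; the documents support only that it would be counted if the list is programmed as printed. Nothing in 10.3.3 tells the programmer to ignore the row.

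Presence in 10.3.3 also does not by itself make a code an endpoint. TIA is listed there, and 5.1 does not count it. That is correct, but TIA has its own label by which it can be left out, and this row has none.

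A reader might also infer that any comorbidity entry of the code would trigger an event. That does not follow. 5.1 asks for the SE code as the first listed diagnosis, and none of its five fields is named as comorbidity. The sub-disease and second-most-resources fields sit awkwardly with that requirement, so the point is ambiguous at most.

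Finally, being listed under peripheral vascular disorder does not on its own exclude a code from SE: I742, I743 and I745 appear in both 10.3.1 blocks. What remains is that the note names a stenosis, and that the 10.3.1 SE list omits it.

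**Conclusion.** The concern holds as an unresolved contradiction in the code list behind the primary effectiveness endpoint. Read as printed, 10.3.3 admits a non-embolic condition to SE and to the composite, against the SAP's own SE list in 10.3.1.

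The bias would be toward 1, provided the stenosis codes occur at similar rates in both arms after weighting. Its size is unknown. The hazard ratios of about 0.73 and 0.78 for SE, and the composite figures, rest on assumed shares with no basis in the documents. For the composite the effect is probably small: 0.703 to 0.706 against 0.700 if 1% to 2% of warfarin-arm events are affected.

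It would go too far to conclude that the primary comparison is materially distorted or that the sample size must change. No figure in the documents supports either, and the stated design figures reproduce. The correction is still worth making, because a primary endpoint definition should not depend on how a programmer reads an empty cell.

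**What to change.** Delete the I748 subclavian stenosis row from 10.3.3, or label it there as peripheral vascular disorder and not an endpoint. Then check that the systemic embolism lists in 10.3.1 and 10.3.3 are identical row for row. If the programs have already been run, confirm whether the code was counted and, if it was, rerun the SE and composite analyses without it.

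The cost is one row and a line in the SAP version history. The protocol names SE without listing codes, so the change brings the code list into line with the stated endpoint and does not redefine it. Removing the TIA rows from 10.3.3 is optional tidying and changes no result.

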Procedure for definition of "bleeding"

Step 1. To extract the following group A or group B from MDV data base.

Group A: ICD-10 name includes "出血 (bleeding)" or "血腫 (ecchymoma)"

Group B: Disease name includes "出血 (bleeding)" or "血腫 (ecchymoma)"

Step 2. To select disease names considered to be relevant to side effect of OAC individually from disease names excluded in Step 1.

Step 3. To exclude disease names which are not considered to be relevant to side effect of OAC from the disease names included in Step 1.

ICD-10	ICD10Name
A162	Tuberculosis of lung, without mention of bacteriological or histological confirmation
A165	Tuberculous pleurisy, without mention of bacteriological or histological confirmation
B303	Acute epidemic haemorrhagic conjunctivitis (enteroviral)
D500	Iron deficiency anaemia secondary to blood loss (chronic)
D62	Acute post haemorrhagic anaemia
D66	Hereditary factor VIII deficiency
D683	Haemorrhagic disorder due to circulating anticoagulants
D698	Other specified haemorrhagic conditions
D699	Haemorrhagic condition, unspecified
E078	Other specified disorders of thyroid
E274	Other and unspecified adrenocortical insufficiency
G361	Acute and subacute haemorrhagic leukoencephalitis [Hurst]
G951	Vascular myelopathies
G968	Other specified disorders of central nervous system
H052	Exophthalmic conditions
H113	Conjunctival haemorrhage

ICD-10	ICD10Name				
H168	Other keratitis				
H208	Other iridocyclitis				
H210	Hyphaema				
H313	Choroidal haemorrhage and rupture				
H350	Background retinopathy and retinal vascular changes				
H356	Retinal haemorrhage				
H357	Separation of retinal layers				
H405	Glaucoma secondary to other eye disorders				
H431	Vitreous haemorrhage				
H448	Other disorders of globe				
H470	Disorders of optic nerve, not elsewhere classified				
H603	Other infective otitis externa				
H669	Otitis media, unspecified				
H738	Other specified disorders of tympanic membrane				
H922	Otorrhagia				
I213	Acute transmural myocardial infarction of unspecified site				
I230	Haemopericardium as current complication following acute myocardial infarction				
I312	Haemopericardium, not elsewhere classified				
I600	Subarachnoid haemorrhage from carotid siphon and bifurcation				
I601	Subarachnoid haemorrhage from middle cerebral artery				
I602	Subarachnoid haemorrhage from anterior communicating artery				
I603	Subarachnoid haemorrhage from posterior communicating artery				
I604	Subarachnoid haemorrhage from basilar artery				
